Primary	Red blood cell transfusion independence (RBC-TI) for 12 weeks (84 days) with a mean hemoglobin increase ≥ 1.5 g/dL	Proportion of subjects who are RBC transfusion-free for any 12-week period associated with a concurrent mean hemoglobin increase ≥ 1.5 g/dL compared to baseline	Week 1 through Week 24
Secondary	Red blood cell transfusion independence (RBC-TI) for 24 weeks	Proportion of subjects who are RBC transfusion-free from Week 1 through Week 24	Week 1 through Week 24
	Mean hemoglobin change over 24 weeks	Mean hemoglobin change over the 24-week period of Week 1 through Week 24 compared to baseline	Week 1 through Week 24
	Hematologic improvement – erythroid response (HI-E) per IWG (Cheson, 2006)	Proportion of subjects achieving HI-E over any consecutive 56-day period	Week 1 through Week 24
	Time to HI-E	Time from first dose to first onset of achieving HI-E	Week 1 through Week 24
	RBC-TI for ≥ 12 weeks (84 days)	Proportion of subjects who are RBC transfusion-free over a consecutive 84-day period	Week 1 through Week 24
	Duration of RBC-TI ≥ 12 weeks (84 days)	Maximum duration of RBC transfusion independence for subjects who achieve RBC-TI ≥ 84 days	Week 1 through End of Treatment
	Time to RBC-TI ≥ 12 weeks (84 days)	Time from first dose to first onset of transfusion independence ≥ 84 days	Week 1 through Week 24
	Time to first RBC transfusion	Time from first dose to first transfusion on treatment	Week 1 through End of Treatment
	RBC transfusion burden on treatment	Total number of RBC units transfused on treatment	Week 1 through Week 24
	RBC-TI for ≥ 56 days (8 weeks)	Proportion of subjects who are RBC transfusion-free over a consecutive 56-day period	Week 1 through Week 24
	RBC-TI for a consecutive 24-week period	Proportion of subjects who are RBC transfusion-free for a consecutive 24-week period in the first 48 weeks from first dose	Week 1 through Week 48
	Health-related quality-of-life (HRQoL)	Evaluation of EORTC QLQ-C30 score and FACT-An	Screening through Week 24
	Safety	Type, frequency, severity of AEs and relationship of AEs to luspatercept/epoetin alfa	Screening through 42 days post last dose; Randomization through Week 48

Table 2: Study Endpoints

Endpoint	Name	Description	Timeframe
Secondary (continued)	PK parameters	Serum luspatercept concentrations and PK parameters	Randomization through 1 year post first dose
	Antidrug antibodies (ADA)	Frequency of antidrug antibodies	Randomization through 1 year post first dose

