The Post-treatment Follow-up Period consist of the 42-Day Safety Follow-up (Section 6.3.1), which includes (but is not limited to) the collection of adverse events (AEs), concomitant drugs and RBC-transfusion data, and the Long-term Follow-up (Section 6.3.2).

The transfusion data collection will continue until 8 weeks from the date of last dose of IP or from the date of the EOT Visit (whichever is later).

[figure not shown]
In addition, continuation of monitoring for other malignancies/pre-malignancies and progression to AML will occur in the Long-term Post-treatment Follow-up Period along with data collection of subsequent MDS therapies, and overall survival for 5 years from the date of the first dose of IP, or 3 years from the last dose (whichever occurs later), unless the subject withdraws consent from the study, dies or is lost to follow-up. For that purpose, visits (which may consist of telephone contacts from the site) will be conducted every 12 weeks for the first 3 years from the date of last dose of IP and every 6 months thereafter, if applicable.

An antidrug antibodies (ADA) sample(s) may be required in the Post-treatment Follow-up Period for subjects assigned to the luspatercept arm, who terminate the Treatment Period with less than 1-year of ADA monitoring if a subject is ADA positive at the time of treatment discontinuation.

Data Monitoring Committee (DMC)/Steering Committee (SC)

An external, independent DMC comprised of experts in MDS not involved in the ACE-536-MDS-002 study as well as a SC comprised of study investigators and sponsor representatives will be established. For details on composition and roles please refer to [Section 9.10.4](#) and [Section 9.10.5](#), respectively.

Figure 2: Overall Study Design

Abbreviations: AE = adverse event; EOT = End of Treatment; IP = investigational product; MDS = Myelodysplastic syndromes; QW = once every week; Q3W = every 3 weeks; SC = subcutaneous.

¹ Individual epoetin alfa doses according to body weight will be rounded: up to the next 2,000 IU dose level for Starting Dose Level and Dose Level -1, and up to the next 4,000 IU for Dose Level +1 and Dose Level +2 for doses exceeding a calculated dosing of 56,000 IU according to body weight.

² Crossover between the treatment arms is not permitted during the Study Treatment Period.

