6.4.1 Transfusion Assessment

The RBC transfusion data during the 8 weeks immediately preceding randomization will be used to determine the baseline RBC transfusion requirement for an individual study subject.

During the Treatment Phase transfusions will be assessed and recorded in the eCRF on an ongoing basis (prior to each dose of IP) until 8 weeks after last dose of IP or the End of Treatment Visit, whichever occurs later. Clinical site staff must confirm (and document in the subject's source record) if any transfusions were received by the subject (including any transfusions received at institutions outside of the study site in between study visits) prior to each IP administration. In addition to local procedures in place at the site to capture this information, a patient transfusion diary will be provided to subjects and will be reviewed by the site when/if returned by the patient.

Red blood cell transfusions administered for elective surgery, infections or bleeding events will not count toward baseline requirement, efficacy assessment, or progressive disease status but should still be recorded in the eCRF.

The following information will be collected for RBC transfusions (and platelet transfusions if applicable) and reported in the eCRF:

- Type, number of units, reason and date of transfusion
- The Hgb value for which any RBC transfusion is given, and the platelet value for which any platelet transfusion is given, (these Hgb and platelet values may be local or central laboratory measurements)

Please find recommendations for adequate source documentation of transfusion history as well as transfusions given during the treatment phase below:

- Signed original or copy of single transfusion record including number of units administered and Hgb/platelet value prior to transfusion.
- Signed record of multiple transfusions done at the same clinic. For each transfusion, the units and dates are specified along with Hgb/platelet value prior to each transfusion.

- If electronic record: signed print-out of administration record(s), specifying unit(s) on specified date(s), plus signed additional documentation of Hgb/platelet values(s) prior to transfusion.
- Signed referral letter(s) specifying date(s) and number(s) of units administered with Hgb/platelet value(s) prior to transfusion(s).

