9.7.2 Secondary Efficacy Analyses

The secondary efficacy endpoints will be analyzed and reported at the time of the analysis of the primary efficacy endpoints.

Secondary endpoints will be analyzed descriptively, unless otherwise specified, and will be based on the ITT population. Kaplan-Meier methods will be used to estimate curves for time to event secondary variables. Count, percentages, and 95% confidence interval will be used to describe categorical secondary variables.

Gate-keeping method will be used to control the overall Type I error rate for the following secondary endpoints in the order of:

- HI-E response (Week 1 to 24)
- RBC-TI for 24 weeks (Week 1 to 24)
- RBC-TI ≥ 12 weeks (Week 1 to 24)

After the result from the primary efficacy endpoint shows statistical significance, RBC-TI for 24 weeks in Week 1 to 24 will be tested for significance at the one-sided significance level of 0.021 only if both primary endpoint and HI-E response in Week 1 to 24 are significant. RBC-TI ≥ 12 weeks in Week 1 to 24 will be tested for significance at the one-sided significance level of

0.021 only if the results for primary endpoint, HI-E in Week 1 to 24, and RBC-TI for 24 weeks in Week 1 to 24 are all significant. The testing procedure above will be implemented strictly in order to control the overall one-sided Type I error rate of 0.025 due to multiplicity.

Other secondary endpoints will be analyzed without employing methods for controlling the type one error rate. Any statistically significant treatment effect on these secondary endpoints cannot be interpreted as confirmatory, but rather informative.

RBC transfusion independence (RBC-TI) for 24 weeks is defined as the absence of any RBC transfusion from Week 1 to the end of Week 24. Subjects discontinued from the Treatment Phase prior to finishing Week 24 will be counted as non-responders.

Mean hemoglobin change over 24 weeks is defined as the mean hemoglobin change over the 24-week period of Week 1 through Week 24 compared to baseline

Hematologic improvement – erythroid response (HI-E) per IWG (Cheson, 2006) is defined as proportion of subjects meeting HI-E criteria sustained over any consecutive 56-day period over the first 24 weeks from Week 1. Subjects discontinued from the Treatment Period without achieving HI-E will be counted as non-responders.

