Time to HI-E will be summarized only for subjects who achieve HI-E response. It is defined as time from Week 1 to first onset of achieving HI-E. It will be summarized only for subjects who achieve HI-E within the first 24 weeks from Week 1.

RBC-TI for ≥ 12 weeks (84 days) is defined as the proportion of subjects achieving RBC-TI for ≥ 84 days during any consecutive 84-day period from Week 1 through Week 24.

Duration of RBC-TI ≥ 12 weeks (84 days) is defined as the longest RBC-TI period for subjects who achieve RBC-TI ≥ 12 weeks from Week 1 through Week 24. Subjects who maintain RBC-TI through the end of the Treatment Period or at the time of analysis will be censored at the date of treatment discontinuation, date of analysis or death, whichever occurs first.

Time to RBC-TI ≥ 12 weeks (84 days) will be summarized only for subjects who achieve RBC-TI ≥ 84 days from Week 1 through Week 24. It is defined as the time between Week 1 and the date onset of TI is first observed (ie, Day 1 of 84 days without any RBC transfusions).

Time to first RBC transfusion is defined as time from Week 1 to first RBC transfusion on treatment. Subjects who maintain RBC-TI through the end of the Treatment Period or time of analysis will be censored at the date of treatment discontinuation/time of analysis or death, whichever occurs first.

RBC transfusion burden on treatment is defined as total number of pRBC units transfused within the first 24 weeks of treatment since Week 1.

RBC-TI for ≥ 56 days (8 weeks) is defined as the proportion of subjects achieving RBC-TI for ≥ 56 days during any consecutive 56-day period from Week 1 through Week 24.

RBC-TI for a consecutive 24-week period is defined as the proportion of subjects achieving RBC-TI for ≥ 168 days during any consecutive 168-day period from Week 1 through Week 48.

Progression to AML: time to AML progression is defined as the time between randomization and first diagnosis of AML as per WHO classification of $\geq 20\%$ blasts in peripheral blood or bone

marrow. Subjects with diagnosis of AML will be considered to have had an event. Subjects who have not progressed to AML at the time of analysis will be censored at the last assessment date which does not indicate progression to AML.

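### Censoring transfusion-independence duration and time to first transfusion at treatment stop or death may overstate durability; add an analysis using the 8 weeks of post-treatment transfusion data

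*Combined protocol and SAP*

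**What the plan says.** Section 9.7.2 defines duration of RBC-TI ≥ 12 weeks as the longest transfusion-free period among subjects who reach it in Weeks 1 to 24. Subjects still independent at the end of the Treatment Period or at analysis "will be censored at the date of treatment discontinuation, date of analysis or death, whichever occurs first". For time to first RBC transfusion they "will be censored at the date of treatment discontinuation/time of analysis or death, whichever occurs first". The method is stated once: "Kaplan-Meier methods will be used to estimate curves for time to event secondary variables".

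Table 2 in Section 2 runs both endpoints from Week 1 through End of Treatment. It describes the first as "Maximum duration of RBC transfusion independence for subjects who achieve RBC-TI ≥ 84 days" and the second as "Time from first dose to first transfusion on treatment".

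Transfusion recording goes further. Section 3.1 states: "The transfusion data collection will continue until 8 weeks from the date of last dose of IP or from the date of the EOT Visit". The later of those two dates governs. Section 6.3.2 agrees, and Section 6.4.1 has recording continue "until 8 weeks after last dose of IP or the End of Treatment Visit, whichever occurs later". Nothing in Section 9 uses these post-treatment transfusions for either endpoint, and no sensitivity analysis is described there.

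Both endpoints lie outside the gate-keeping sequence. Of such endpoints Section 9.7.2 says: "Any statistically significant treatment effect on these secondary endpoints cannot be interpreted as confirmatory, but rather informative".

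**The concern.** Kaplan-Meier treats a censored subject as someone whose later risk is that of the subjects still under observation. Several reasons for leaving treatment make this doubtful:

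- Section 11.1 lists adverse events, lack of efficacy and disease progression. Appendix D counts a hemoglobin fall of 2 g/dL or more as progression, which is a step towards transfusion.
- Sections 8 and 8.2 take a subject off treatment when an excluded medicine is needed, including another ESA, a hypomethylating agent or lenalidomide.
- Section 1.3.2.4 says that the stopping rules differ between the drugs. Table 5 (luspatercept) has a row for worsening leukopenia, neutropenia or thrombocytopenia that can end in discontinuation; Table 7 (epoetin alfa) has none. Any distortion could therefore differ by arm, in an open-label trial.

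Death is handled as if the subject could still be transfused later.

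At stake is the reported median duration. Section 1.3.1 gives longer RBC-TI as part of the reason for the trial, so this figure will be read closely even without a formal test.

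**Working it through.** **The plan's own figures.** The documents give no expected duration, stopping rate, death rate or post-stop transfusion rate for this trial. The design figure is 90% power with 175 per arm (Section 9.3). It reproduces: log odds ratio = ln[(0.36 × 0.80)/(0.20 × 0.64)] = ln 2.25 = 0.811; SE = √[1/(175 × 0.36 × 0.64) + 1/(175 × 0.20 × 0.80)] = 0.246; power = Φ(0.811/0.246 − 1.96) = 90.9%. It does not depend on the two endpoints discussed here.

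**Model for the effect of stopping (all rates assumed).** No transfusion is possible before week 12, and the on-treatment hazard λ is constant after that. Subjects stop at rate g while still independent. After stopping, the hazard is kλ.

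- For a protocol-rule median of 80 weeks, λ = ln 2/(80 − 12) = 0.01019 per week.
- If 10% stop per year, g = −ln(0.90)/52 = 0.00203. If 30% stop, g = −ln(0.70)/52 = 0.00686.
- If the 8 post-stop weeks are counted, the ratio of recently stopped to on-treatment subjects settles at r = g × (e^(8a) − 1)/a, with a = λ(1 − k) + g.
- The hazard is then multiplied by m = (1 + kr)/(1 + r), and the median is about 12 + ln 2/(λm).

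Worked cases:

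- k = 3, 10% stopping: a = −0.0184, r = 0.0151, m = 1.030, median 78.0.
- k = 10, 30% stopping: a = −0.0849, r = 0.0398, m = 1.345, median 62.6.

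The full calculation, which lets r build up from zero, gives:

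| Post-stop hazard multiple k | Median with the 8 weeks counted, 10% stop/year | Same, 30% stop/year |
|---|---|---|
| 0.5 | 80.5 | 81.8 |
| 1 | 80.0 | 80.0 |
| 3 | 78.1 | 74.2 |
| 10 | 74.0 | 63.4 |

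Against the 80 weeks reported under the protocol rule, the overstatement is −0.5 to −1.8 weeks at k = 0.5 and zero at k = 1. For k from 3 to 10 it is 80 − 78.1 = 1.9 to 80 − 63.4 = 16.6 weeks. For k from 3 to 10, a 40-week median becomes 39.4 to 35.2 and a 120-week median becomes 116.9 to 90.8.

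**Death.** With 5% deaths per year (assumed), d = −ln(0.95)/52 = 0.00099. At k = 1 the median time alive and transfusion-free is 12 + ln 2/(0.01019 + 0.00099) = 74.0 weeks, against 80.0 with deaths censored. The direction is fixed, because counting deaths adds events and never removes any.

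**A harsher scenario.** Suppose 10%, 20% or 30% of responders stop drug and every one of them is transfused within 8 weeks. The protocol rule then estimates a hazard of about λ(1 − f). A true median of 52 is reported as roughly 12 + 40/(1 − f) = 56, 62 and 69 weeks; simulation with 200,000 subjects gives about 56, 61 to 62, and 67 to 68. Adding the 8 weeks returns 52, but only because the scenario places every post-stop transfusion inside that window. If the same shares leave for unrelated reasons, the protocol rule itself returns 52.

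**The case against.** The strongest reply is that the rule is deliberate and consistent. Table 2 limits both endpoints to the time on treatment, so leaving out later transfusions follows from the definition, and counting them would estimate something else. This stands in part: there is no contradiction to repair, and replacing the main definition would be a choice of estimand. But a pure on-treatment duration would end when treatment ends. Kaplan-Meier with censoring at stop or death estimates what would have been seen had nobody stopped or died, and it needs the equal-risk assumption, which the protocol neither states nor defends.

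Other points for the plan also stand:

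- The benefit check at Day 169 and later (Section 6.4.2) cannot remove a subject with no transfusions over 8 weeks. Baseline is 2 to 6 units, so zero units is always a reduction of at least 2. Lost benefit that shows as a transfusion is already an event.
- RBC-TI for 24 weeks, which is gate-kept, counts discontinuation before Week 24 as non-response.
- Section 9.7.2 leaves full details to the SAP. The combined document contains no separate SAP text, so a suitable sensitivity analysis may exist there.

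A reader might infer that durability is overstated as a matter of fact, or by the 8% to 31% that a move from 52 to 56–68 weeks implies. The documents support neither. The direction for stopping depends on the post-stop hazard, and the harsher scenario assumes that every stopper is about to be transfused. Nor does the confirmatory benefit claim rest on these endpoints: the primary endpoint is 12 weeks of independence with a hemoglobin rise within Weeks 1 to 24.

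**Conclusion.** The concern holds in conditional form. The censoring rule may overstate the duration of RBC-TI and the time to first transfusion if subjects who stop are at higher risk than those who continue, and the amount may differ by arm. The effect is nil if the risk is unchanged after stopping, and it reverses if the risk falls, for example after another therapy starts. Only the direction for death is certain, and only relative to being alive and transfusion-free.

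For an 80-week median, the assumed range is about −2 to +17 weeks for stopping, and about 6 weeks for death at 5% per year with k = 1. These figures illustrate sensitivity and do not predict this trial's result. Both endpoints are descriptive; the primary analysis, its alpha and its power do not change. The point is worth acting on because the data that would test the assumption are already being collected.

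**What to change.** Keep the on-treatment analysis as defined. In the SAP, prespecify beside it, for both endpoints, an analysis that:

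- counts as an event any qualifying RBC transfusion through the end of the 8-week post-treatment window (excluding those that Section 6.4.1 already excludes from efficacy), with the end of the window dated as in Sections 3.1 and 6.3.2;
- censors at the end of that window, or earlier at the data cutoff or the start of another MDS therapy;
- treats death as an event or as a competing event, stated in advance.

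Define the date of treatment discontinuation as last dose, decision to stop or EOT visit. With dosing every 21 days in one arm and every 7 in the other, a last-dose date could cut off different amounts of follow-up. Report both results by arm.

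No further data collection is needed. The cost is modest programming and reporting, and possibly shorter reported durations. If the SAP already contains such an analysis, only the date definition needs checking.
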